### 6.4 Blinding and Minimization of Bias

The Phase 1 portion of the trial will be open label. Ten patients will be enrolled in a single cohort that will receive low dose vesigenurtacel-L vaccine ( $1 \times 10^6$  cells) monotherapy. If well-tolerated, the low dose as well as a higher dose ( $1 \times 10^7$  cells) will be advanced to Phase 2.

The Phase 2 portion of the trial will have three blinded (physician-patient), placebo-controlled arms and one open label arm. The placebo has been formulated with an intralipid suspension to visually resemble the vesigenurtacel-L vaccine. Seventy-five patients who will receive BCG will be randomized to low dose vesigenurtacel-L in combination with BCG, high dose vesigenurtacel-L in combination with BCG, or

placebo in combination with BCG; 25 patients who will not receive BCG will be enrolled in an arm that will receive high dose vesigenurtacel-L vaccine monotherapy.

Blinding in Phase 2 was indicated in order to be able to better facilitate ongoing evaluation of safety.

## **7.0 SUBJECT COMPLETION AND WITHDRAWAL**

### **7.1 Subject Completion**

Patients may continue to receive study treatment until they complete the dosing phase of the study or meet the criteria for treatment discontinuation described in Section 7.2.1.

### **7.2 Subject Withdrawal from Study**

In accordance with International Conference on Harmonization (ICH) Good Clinical Practice (GCP) Guidelines, a patient has the right to withdraw from the study at any time for any reason without prejudice to his/her future medical care by the physician or at the institution. The investigator and sponsor also have the right to withdraw patients from the study treatment, as described below or for safety, behavioral, or administrative reasons.

#### **7.2.1 Discontinuation from Study Treatment**

Every effort must be made by study personnel to keep patients on study treatment. However, a patient **will** be discontinued prior to completion of the study treatment for any of the following reasons:

- Grade 4 adverse event related to study product (or Grade 3 adverse event at the Principal Investigator's discretion).
- Suspected Unexpected Adverse Drug Reaction, which requires patient unblinding
- Grade 3 or greater allergic reaction or autoimmune reaction
- Progressive disease
- Pregnancy
- Termination of the study by Heat Biologics
- Concurrent illness that prevents further administration of treatment

Patients **may** also be discontinued prior to completion of the study treatment for any of the following reasons:

- Recurrent disease (Patients with recurrent disease at an assessment may continue on treatment if judged by the investigator to be in the patient's best interest.)
- Significant deviation from protocol on the part of the patient (includes lack of compliance)
- Significant protocol violation on the part of the investigator

The explanation of why the patient is discontinuing study treatment should be documented in the ECRF. If the patient discontinues study treatment due to toxicity, "Adverse Event" will be recorded as the primary reason for withdrawal. If a patient is prematurely discontinued from the study at any time due to an AE or

SAE, the patient must be followed until resolution to Grade 2 or less, unless it is unlikely to improve because of underlying disease.

### **7.2.2 Discontinuation from Study Follow-Up**

If a patient prematurely discontinues study treatment for any reason, the patient will continue to be followed for study endpoints, unless consent for this is specifically withdrawn. If the patient withdraws consent for continued follow up, the investigator must make every effort to perform the EOT assessments four weeks following the last dose of study product, even if the patient has initiated other anticancer treatment.

### **7.2.3 Lost to Follow-Up**

If a patient fails to return for the necessary visits or discontinues prematurely from treatment, a genuine effort should be made to determine the reason why. For a patient lost to follow-up there should be at least two documented attempts to contact the patient.

### **7.2.4 Replacement of Subjects**

Patients will not be replaced. A 10% overage of patients has been included in the sample size to allow for patients who discontinue for reasons other than evidence of disease or toxicity or who are missing data.

## **8.0 INVESTIGATIONAL PRODUCT**

All production, formulation, and packaging of the investigational agent will be in accordance with applicable current Good Manufacturing Practice (cGMP) and meet applicable criteria for use in humans.

### **8.1 Description of Investigational Product, Vesigenurtacel-L**

Vesigenurtacel-L is a cell line derived from a human cancer cell line, designated as PC3. The cell line was transfected with the plasmid cDNA 'B45-neo-gp96Ig-HLA A1'. Vesigenurtacel-L has been irradiated to render cells replication incompetent while maintaining biological activity; i.e., expression of certain proteins.

Manufacturing of vesigenurtacel-L includes expansion of batches of cells with testing for presence of expression of HLA-A1 by fluorescence-activated cell sorter and gp96-Ig by enzyme-linked immunosorbent assay (ELISA). Cells are harvested, washed, resuspended in buffer, and irradiated at 12,000 rad.

The vesigenurtacel-L vaccine to be injected will contain irradiated cells expressing HLA-A1 on at least 70% of the cells and produce  $\geq 60$ ng gp96-Ig/24h x 1 million cells; the cells will have  $\geq 70\%$  viability by trypan blue exclusion.

Vesigenurtacel-L is provided as frozen, single-dose vials either 1) as concentrated frozen liquid, which will require dilution by the pharmacist with sterile saline, or 2) as fully-diluted frozen liquid not requiring additional dilution. In either case the final drug product will consist of cells resuspended in buffered saline containing human serum albumin (HSA), dimethyl sulfoxide (DMSO), and pentastarch and will be delivered at doses of either  $1 \times 10^6$  cells or  $1 \times 10^7$  cells. Overfill is factored into each vial to allow extraction of the full dose for patient administration. Refer to the Pharmacy Manual for instructions for preparation and labeling.

## 8.2 Description of Placebo

A challenge for cell-based immunotherapy is the development of a placebo control that is safe for use in patients and which mimics the appearance and biophysical properties of intact cells in solution. Toward this end, we will utilize a diluted suspension of Intralipid (Baxter), which is FDA approved for use in humans. This Intralipid solution will be diluted to a final concentration of 0.15% in a buffered saline solution also containing HSA, DMSO, and pentastarch, but lacking vesigenurtacel-L cells. This solution closely resembles the appearance and viscosity of the vesigenurtacel-L vials used in the experimental arms of the study.

Intralipid solution is contraindicated in patients with a soy, egg, or peanut allergy.

## 8.3 Dosage and Administration of Vesigenurtacel-L and Placebo

At each dosing visit for Phase 2, the site must contact the IWRS for assignment of the dose vial. Study product will be administered intradermally. Each dose will be divided into the number of injections required to reach the number of cells per dose with no more than 0.1 mL per injection (approximately 4-6 injections), and administered as spatially divided intradermal injections separated by approximately 4-5 cm in the same extremity to increase volume distribution and enhance antigen presentation to lymph node regions shared with the urinary bladder. Dosing will rotate injection site extremities every four timepoints: antero-lateral left thigh, antero-lateral right thigh, left buttock, and right buttock. Injection sites will be recorded and retained in the patient records. If injection site reactions are reported as an AE, an alternative injection site may be used upon discussion with the sponsor.

Missed doses may be made up depending on the timing of the dosing, after discussion with the sponsor.

## 8.4 Dosage and Administration of BCG (Phase 2)

A full dose of BCG according to the investigator's standard practice should be administered intravesically, unless dose reductions are deemed appropriate by the investigator to manage toxicity. The induction phase consists of 6 weekly doses, and the maintenance phase includes three once-weekly doses at 3, 6, and 12 months since the start of induction BCG. Patients who receive 5 of 6 induction doses may continue to receive study product and maintenance BCG.

Additional information can be found in the package inserts:

(<http://www.fda.gov/downloads/BiologicsBloodVaccines/CellularGeneTherapyProducts/ApprovedProducts/UCM310364.pdf> and [http://www.merck.com/product/usa/pi\\_circulars/t/tice\\_bcg/ticebcg\\_pi.pdf](http://www.merck.com/product/usa/pi_circulars/t/tice_bcg/ticebcg_pi.pdf)).

Dose reductions will follow those as defined in Section 8.5.2.

## 8.5 Treatment Assignment

The definitions of the randomized arms relative to the intended intervention to be used in those arms will be as follows:

Phase 1: Vesigenurtacel-L Low Dose:  $1 \times 10^6$  cells per dose

Phase 2:

- Arm 1: Vesigenurtacel-L consisting of  $1 \times 10^6$  cells per dose + BCG

- Arm 2: Vesigenurtacel-L consisting of  $1 \times 10^7$  cells per dose + BCG
- Arm 3: Placebo (containing intralipid for blinding, but no cells) + BCG
- Arm 4: Vesigenurtacel-L consisting of  $1 \times 10^7$  cells per dose

[figure not shown]
In Phase 2, patients who will receive BCG will be randomized centrally to Arm 1, 2, or 3 using a stratified block design according to risk of recurrence (strata: high vs. intermediate risk) and CIS (strata: yes vs. no). Patients who will not receive BCG will be enrolled in Arm 4.

Due to delays in the batch release of certain doses of vaccine, the randomization schedule may be temporarily revised from a 1:1:1 randomization to a 1:1 randomization, with one arm being briefly suspended. During the period of revised randomization, each patient will maintain at least a 50% chance of receiving vaccine versus placebo. Randomization strata will remain unchanged. Upon batch release of the vaccine the randomization will return to the original 1:1:1 ratio. In order to maintain the study blinding, temporary closure of certain arms will not be disclosed outside of the DMC except as needed for Informed Consent documents.

### 8.5.1 Schedule and Duration of Treatment

The dose administration will follow the regimen outlined in Figure 2 below.

**Figure 2. Dosing Schedule**

In Phase 1, each patient will receive intradermal injections of vesigenurtacel-L weekly for 12 doses (doses administered on Weeks 1-6 with a vaccine holiday on Week 7 to allow for disease assessment, followed by Weeks 8-13), then monthly for 3 doses for up to a total of 15 doses, unless the criteria for treatment discontinuation are met. Vesigenurtacel-L should be administered within the allowable windows of the

scheduled dose. In Phase 2, each patient in Arms 1-3 will receive weekly intradermal injections of blinded study product in combination with intravesical induction BCG for 6 weeks followed by 6 weeks of blinded study product monotherapy with a vaccine holiday on Week 13 to allow for disease assessment, followed by three courses of three once-weekly injections in combination with intravesical maintenance BCG for a total of 21 doses, unless the criteria for treatment discontinuation are met. Patients in Arm 4 will receive weekly intradermal injections of vesigenurtacel-L for 12 doses, followed by three courses of three once-weekly injections for a total of 21 doses, unless the criteria for treatment discontinuation are met.

### **8.5.2 Dose Modifications**

Dose modifications of vesigenurtacel-L will not be permitted during the trial.

BCG should be given at full strength with dose reductions as needed for management of toxicity according to the investigator's standard of care.

## **8.6 Study Product Handling and Accountability**

### **8.6.1 Preparation**

Vesigenurtacel-L and placebo must be thawed and labeled prior to injection. In addition, certain batches will require dilution with sterile saline. Preparation of the product and labeling procedures will be described in the Pharmacy Manual.

### **8.6.2 Labeling**

Study product will be labeled with the product name/placebo, the vial number, storage conditions, and other local regulatory requirements.

### **8.6.3 Storage**

Vesigenurtacel-L and placebo must be stored at  $\leq -120^{\circ}\text{C}$  in the vapor phase of a liquid nitrogen dewar. If liquid nitrogen storage is not available at the investigative site, a unit will be supplied by the study sponsor. The sponsor will also arrange for replacement of the liquid nitrogen at regular intervals to ensure that the proper storage temperature is maintained throughout the study.

### **8.6.4 Product Accountability**

The investigator or designee (where applicable) will be responsible for study product accountability, reconciliation, and record maintenance. In accordance with all applicable regulatory requirements, the investigator or designated site staff (e.g., investigational drug pharmacist) must maintain current investigational product accountability records throughout the course of the study. These records will contain the following information:

- Patient Study ID number
- Date, quantity, and vial number of agent received, dispensed, administered, lost, and destroyed
- Documentation of storage conditions

These inventories must be made available for inspection by the study monitor. The investigator will be responsible for ensuring that all used and unused trial supplies are accounted for. At the end of the trial the

study monitor will also collect the investigational agent dispensing record. A copy of the dispensing record should be kept at the site and maintained with the study records.

## **8.7 Treatment of Investigational Product Overdose**

As this is the first patient trial with vesigenurtacel-L, there have been no cases of overdose. Treatment of any suspected or confirmed overdose with vesigenurtacel-L should be symptomatic, and supportive care is recommended in cases where overdose is suspected. As described in the Investigator's Brochure for vesigenurtacel-L, Heat Biologics does not recommend specific treatment for overdose or toxicity; however, the investigator should use appropriate clinical judgment in treating the overdose. For the purposes of this study, an overdose of vesigenurtacel-L is defined as any dose 50% greater than the intended dose for that patient. Appropriate supportive care measures would need to be provided to address these potential toxicities in the event of an overdose.

## **8.8 Occupational Safety**

Precautions should be taken to avoid direct contact with the investigational product. A Material Safety Data Sheet (MSDS) describing occupational hazards and recommended handling precautions will be available to the investigator.

## **9.0 CONCOMITANT MEDICATIONS AND NON-DRUG THERAPIES**

### **9.1 Permitted Medications and Non-Drug Therapies**

A single dose of mitomycin C or other standard intravesical treatment administered immediately post-TURBT (for the current occurrence of non-muscle invasive bladder cancer) is permitted according to the investigative center's standard practice.

Maintenance BCG per the institution's standard of care may be administered to patients in Phase 1 at any time. Additional courses of maintenance BCG may be administered to patients in Phase 2 after the completion of study treatment per the protocol.

All concomitant medications, including prescription and over-the-counter medications, taken during the 14 days before the date of first dose, during the study treatment, and through 4 weeks post the last dose of study product will be documented. Any concomitant medication(s), including herbal or vitamin preparations, taken during the study will be recorded in the ECRF. At a minimum, the drug name, dose, and the dates of administration will be recorded. Caffeine consumption will also be collected.

Local and/or systemic injection reactions may be treated with anti-allergics, antipyretics, and/or analgesics in accordance with standard local practice and investigator's clinical judgment.

Pre-treatment of the vaccine injection site with anesthetic cream is allowed only after the Week 1 vaccine administration has been performed without it and injection pain has been documented as an AE.

Repeat TURBT or fulguration procedures will be permitted only in the setting of persistent, recurrent, or progressive disease according to an investigator's standard practice.

### **9.2 Prohibited Medications and Non-Drug Therapies**

Prohibited concomitant medications include chronic use of systemic corticosteroids or other immunosuppressant medications. Topical and inhalation steroids will be permitted. No concomitant chemotherapy, immunotherapy (other than BCG according to the protocol schedule), immunosuppressive or other anti-cancer therapy will be permitted prior to progression/recurrence or study withdrawal for other reasons.

Administration of other concomitant investigational agents for any indication, other than the vesigenurtacel-L vaccine, is not permitted in the treatment phase of this study and for 30 days prior to first dose.

During long-term follow-up there are no prohibited medications, and patients may enroll in any investigational study for which they are eligible.

### **9.3 Supportive Care**

Patients should receive full supportive care during the study, including transfusions of blood and blood products, and treatment with antibiotics, antiemetics, antidiarrheals, and analgesics, and other care as deemed appropriate, and in accordance with their institutional guidelines. Please see Section 9.2 for prohibited medications.

## **10.0 ASSESSMENT OF EFFICACY**

### **10.1 Evaluation of Disease**

Monitoring for disease status via cystoscopy, cytology, and biopsy if indicated, will be conducted every 3 months during treatment and follow up for 2 years then every 6 months for up to a year per SOC. Disease-free status is defined as no evidence of disease, which in turn is defined as negative cytology, negative cystoscopy, and negative biopsy if clinically indicated.

Recurrence is defined as disease that has recurred to the same extent of disease (i.e. same stage/severity) or to a lower stage/severity of disease compared to screening.

Persistent disease is defined as evidence of CIS disease by 6 months for patients with CIS at screening.

Progression is defined as an increase in T stage from CIS or Ta (at screening) to T1 (lamina propria invasion), development of T2 or greater or lymph node (N+) disease or distant metastasis (M1), or an increase in grade from low to high per the IBCG recommendations.

The stage of disease at the time of recurrence or progression will be captured to distinguish between recurrence to the same extent of disease as at screening (i.e. the same stage/severity) versus recurrence to a lower stage/severity of disease at screening versus persistent disease for CIS versus progression.

The date of confirmation of recurrence or progression is defined as the earliest date on which the diagnosis had been made based on the findings of cystoscopy, urinary cytology, or some other diagnostic imaging technique regardless of whether the patient continues treatment. For the purpose of clarity, in the situation where a patient with CIS documented at screening has evidence of CIS at the 3-month assessment, continues treatment, and still has evidence of CIS at 6 months, that patient will be assumed to have persistent disease from the date of randomization.

For intermediate-risk patients (i.e. without CIS) who have evidence of disease at the 3-month assessment, continue treatment, and still have evidence of disease at 6 months, the date of recurrence would be the date of the 3-month assessment.

If requested, the cystoscopy and cytology reports and images may be appended to the ECRF with all patient identifier information removed and the study site and patient study number written on the report, which is to be signed and dated by the investigator.

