#### **12.5.1 Primary Efficacy Analysis**

##### **12.5.1.11-year Disease-Free Survival (1-yr DFS)**

One-year disease-free survival will be defined as the proportion of patients who are free from recurrent disease, progressive disease, and alive one year after the date of randomization/treatment assignment (Arm 4).

For the primary efficacy evaluation, disease-free survival at one year between the experimental groups and the control will be presented as the absolute difference in proportions, as well as the OR, with the associated 95% CI.

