##### **12.5.2.4 Overall disease-free survival**

Overall DFS is defined as the interval between the date of disease recurrence, progression, or death (whichever occurs first) and the date of randomization/treatment assignment (Arm 4) for patients without CIS. For patients with CIS at screening who have persistent disease at 6 months, the date of disease persistence will be defined as the date of randomization/treatment assignment (Arm 4) (i.e. DFS = zero).

Patients with CIS at screening who are disease-free by 6 months will have their overall DFS interval calculated between the date of disease recurrence, progression, or death (whichever occurs first) and the earliest date that the patient was determined to be disease-free. Patients will be censored at the last time of contact if recurrence, progression, or death has not been confirmed at the time of the analysis. Overall DFS will be analyzed using a log-rank test with a term for treatment assignment. In addition, Kaplan-Meier curves will be produced separately for each treatment group. The weighted log rank test will also be applied in an exploratory manner.

In a supporting analysis, a simple Cox proportional hazards model with treatment group as the sole independent variable will be built in order to estimate the hazard rate (HR) and 95%CI for overall DFS between the low and high dose vesigenurtacel-L groups relative to the control. A HR of less than one will provide initial evidence of a favorable outcome with vesigenurtacel-L. These analyses will be completed for the ITT and Per-Protocol populations.

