2.1 Study Objectives

Primary Objective

- **Phase 1:** To characterize the safety and tolerability of monotherapy vaccination with HS-410 in patients with non-muscle invasive bladder cancer.
- **Phase 2:**
 - Arms 1, 2, and 3: To evaluate 1-year disease-free survival in patients with non-muscle invasive bladder cancer treated with BCG in combination with blinded study product (one of two doses of vesigenurtacel-L or placebo).
 - Arm 4: To evaluate 1-year disease-free survival in patients with non-muscle invasive bladder cancer treated with high dose vesigenurtacel-L monotherapy.

Secondary Objectives

Both Phases:

- To evaluate the proportion of patients with recurrence at 3, 6, 12, 18, and 24 months
- To evaluate the proportion of patients with progressive disease at 3, 6, 12, 18, and 24 months
- To evaluate overall disease-free survival
- To evaluate overall survival (OS)
- To evaluate the proportion of patients undergoing post-treatment TURBT or fulguration by 12 and 24 months
- To evaluate the proportion of patients undergoing cystectomy by 12 and 24 months
- To evaluate the proportion of patients with immunologic response of PBMCs via intracellular cytokine staining (ICS) by flow cytometry and/or ELISPOT on CD8+ cells following vesigenurtacel-L vaccination

Phase 2 only:

- To evaluate the safety of the combination of vesigenurtacel-L and BCG
- To evaluate the safety of high dose vesigenurtacel-L monotherapy

Primary Endpoint

- **Phase 1:** Safety and tolerability of monotherapy vaccination with HS-410 in patients with non-muscle invasive bladder cancer.
- **Phase 2:** 1-year disease-free survival in patients with non-muscle invasive bladder cancer treated with BCG in combination with one of two doses of HS-410 or placebo, or with high dose HS-410 without BCG. The 1-year disease-free survival rate is defined as the proportion of patients who are alive and free from recurrence and progression at 12 months following randomization.

Secondary efficacy endpoints:

Both Phases:

- Proportion of patients with recurrence at 3, 6, 12, 18, and 24 months from randomization, estimated based on Kaplan-Meier curves. Recurrence is defined as disease that has recurred to the same extent of disease (ie same stage / severity) or to a lower stage/severity of disease compared to screening.

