7.1 Primary Efficacy Analysis

The primary efficacy parameter is 1 year DFS and will be conducted on the ITT population. It will be calculated as the proportion of patients in the experimental groups and the control who remain disease free at 1 year. Hypothesis testing on the primary endpoint will be done one-sided at a level of significance of $\alpha = 0.10$ using Fisher's exact test. The absolute difference in proportions, as well as the odds ratio, with the associated 95% confidence intervals will also be presented.

The following rules will be used to determine whether a patient is disease free at 1 year or not

- If a patient has a recurrence before day 394 (ie day 366+28 days) or has dropped out of the study before day 394, then the patient is considered to be not disease free at 1 year.
- If a patient is shown to be free from disease on day 366 +/- 28 days, then the patient is considered to be disease free at 1 year.
- If a patient has no recurrence before day 338 (ie day 366-28 days) and after day 394 (day 366+28 days), then the patient is considered to be disease free at 1 year.

If the analysis of the primary endpoint does not suggest any dose response effect between the two vaccine arms, an exploratory analysis will be conducted where the two vaccine arms will be pooled and compared to the control arm for the primary endpoint (proportion of patients alive and disease-free at one year). The outcome will be presented as OR with 95% CI relative to the control group.

In an additional exploratory analysis, the proportion of patients whose disease has recurred to a lower stage than at screening and the proportion of patients whose disease has recurred to the same extent (or greater) as at screening will be compared between the experimental and control groups and presented as an OR with 95% CI.

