7.2 Secondary Efficacy Analyses

For time-to-event endpoints (e.g. DFS, OS), Kaplan-Meier / product limit method will be used to estimate the survival distributions over time, and to estimate median time to event. Where appropriate, inference for time-to-event endpoints will be assessed using the Log-rank test statistic, and the treatment effect will be estimated using Cox proportional hazards model. The assumption of proportional hazards will be assessed graphically.

The following will be analysed using Kaplan-Meier time-to-event methodology:

- Time To Recurrence, defined as the time from randomization to recurrence.
 - Recurrence is defined as disease that has recurred to the same extent of disease (ie same stage / severity) or to a lower stage/severity of disease compared to screening.
 - If recurrence has not occurred in a patient, the date of last disease assessment will be used as the timepoint for censoring.
 - The analysis will be repeated in an exploratory manner where recurrence is defined as only those recurrences to the same extent of disease (or greater) as screening.

- Time To Progression, defined as the time from randomization to progression.
 - Progression is defined as an increase in T stage from CIS or Ta (at screening) to T1 (lamina propria invasion), development of T2 or greater or lymph node (N+) disease or distant metastasis (M1), or an increase in grade from low to high per the IBCG recommendations..
 - If progression has not occurred in a patient, the date of last disease assessment will be used as the timepoint for censoring.

- Disease-Free Survival, defined as the time from randomization to recurrence or progression.
 - If a patient has recurred or progressed, then the first date the recurrence or progression has occurred will be used as the timepoint for the event.
 - If a patient has neither recurred nor progressed, then the date of last disease assessment will be used as the timepoint for censoring.

- Overall Survival, defined as the the time from randomization to death.
 - If a patient is still alive, then the patient will be censored on the date of most recent date known alive.
 - If a patient is lost to follow up, then the patient will be censored on the date last known alive.

- Time to cystectomy, defined as the time from randomization to cystectomy.
 - If a patient has not undergone cystectomy, the patient will be censored on the date of last disease assessment.

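### CIS still present at 6 months is evidently meant to fail DFS from randomization, but the 1-year DFS rules and SAP 7.2 do not carry that rule over

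*Protocol*

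**What the plan says.** **Persistent CIS.** Protocol 10.1 gives persistent disease its own definition, limited to patients who entered with CIS and still have it by 6 months. If such a patient had CIS at 3 months, stayed on treatment and "still has evidence of CIS at 6 months, that patient will be assumed to have persistent disease from the date of randomization". For overall DFS, protocol 12.5.2.4 states that "the date of disease persistence will be defined as the date of randomization/treatment assignment (Arm 4) (i.e. DFS = zero"). A patient with CIS at screening who is clear by 6 months gets credit, with the DFS clock starting at the first disease-free assessment. Protocol 3.1 adds that, although treatment may go on in the presence of disease, the analysis of disease-free status follows 10.1.

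**1-year DFS.** Protocol 12.5.1.1 counts patients who are "free from recurrent disease, progressive disease, and alive one year after the date of randomization/treatment assignment". SAP 2.1 uses the "proportion of patients who are alive and free from recurrence and progression at 12 months following randomization". SAP 7.1 then gives three scoring rules:

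- Rule 1 (failure): "If a patient has a recurrence before day 394 (ie day 366+28 days) or has dropped out of the study before day 394".
- Rule 2 (success): "If a patient is shown to be free from disease on day 366 +/- 28 days".
- Rule 3 (success): no recurrence before day 338 and none after day 394.

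**DFS as time to event.** SAP 7.2 has "Disease-Free Survival, defined as the time from randomization to recurrence or progression", and "If a patient has neither recurred nor progressed, then the date of last disease assessment will be used as the timepoint for censoring". Protocol 12.5.2.3 and the overall DFS entry in SAP 2.1 use the same short definition. The SAP contains no rule for persistent disease.

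**The concern.** Section 10.1 defines persistent CIS separately from recurrence and progression, and neither the 1-year DFS definitions nor SAP 7.1 name it. One patient can therefore be a success on the primary endpoint and a failure at time zero on overall DFS. SAP 7.2, programmed as written, would not reproduce the overall DFS that protocol 12.5.2.4 describes. Two careful analysts could score the same patient differently, both in the randomized comparison and in the Arm 4 estimate of 1-year DFS, which is also a primary objective. With 25 patients per arm, a disagreement about one patient is visible in the result.

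**Working it through.** **Can the case occur?** Take a patient with CIS at screening, Week 13 and Week 25. Section 6.2.3.8 lets the investigator continue treatment, section 9.1 allows repeat TURBT or fulguration for persistent disease, and cystoscopy follows at Weeks 37 and 49. Suppose both are negative.

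**Which SAP 7.1 rule applies?** Week 49 is day 337 ± 3 from first dose, and SAP 3.5 allows up to 3 days between randomization and first dose. From randomization, the visit falls between 337 − 3 + 0 = day 334 and 337 + 3 + 3 = day 343. The rule 2 window runs from 366 − 28 = 338 to 366 + 28 = 394. A negative result on days 338 to 343 meets rule 2. One on days 334 to 337 falls to rule 3, which this patient meets if no recurrence is found after day 394.

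**The same patient under each rule, read literally:**

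| Source | Result |
|---|---|
| Protocol 10.1 and 12.5.2.4 | Persistent disease from randomization; DFS = 0 |
| Protocol 12.5.1.1, SAP 2.1 (1-year DFS) | No recurrence, progression or death: disease free |
| SAP 7.1 rule 1 | No recurrence, no drop-out: not a failure |
| SAP 7.1 rule 2 or 3 | Disease free at 1 year |
| Protocol 12.5.2.3, SAP 2.1 (overall DFS) | No event |
| SAP 7.2 | Censored at last disease assessment |

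**Design figure.** SAP section 4 gives 60% in control, a 30-point difference, one-sided alpha 0.10 and 69/3 = 23 evaluable per arm. Exact power of Fisher's test is the sum, over all tables with p ≤ 0.10, of Bin(x; 23, 0.60) × Bin(y; 23, 0.90). This gives 80.8%, which reproduces the stated 80%. With all 25 per arm it is 84.2%.

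**What one patient is worth.** 1/25 = 4.0 points. For single tables (control vs vaccine, one-sided Fisher), 16/25 vs 21/25 gives p = 0.098. Crediting one more control patient, 17/25 vs 21/25, gives p = 0.160. Likewise 15/25 vs 20/25 gives p = 0.108, and 15/25 vs 21/25 gives p = 0.057.

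**How often one rescored patient changes the verdict** (25 per arm, conditional on such a patient existing):

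| True rates | Power | Control failure rescored: positive to negative | Vaccine failure rescored: negative to positive |
|---|---|---|---|
| 60% vs 90% | 84.2% | 8.7% | 7.8% |
| 54% vs 81% (each × 0.9, drop-outs as failures) | 68.9% | 10.5% | 11.2% |

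With 60% in both arms, the last figure is 4.4%. These rates hold for any single misclassified patient at this sample size. They do not estimate how often this gap will matter.

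**Effect on the reported rate.** The documents give neither the share of patients with CIS nor the share persistent at 6 months and later clear. Purely as an assumption, take 10 to 40% and 10 to 30%. Scoring these patients as failures then lowers 1-year DFS by between 0.10 × 0.10 = 1 point and 0.40 × 0.30 = 12 points, or 0.25 to 3 patients per arm of 25. If both arms fell equally from 60% and 90%, power at 23 per arm would be between 79.7% and 69.9%.

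**The case against.** The best reply is that the intent is not in doubt. Section 3.1 deals with exactly this situation and sends the analysis to 10.1, which calls the disease persistent from randomization. That stands, and it is why the fix should score failure. It does not settle the matter alone: 10.1 defines disease-free status by negative tests, which this patient meets at 1 year, and the SAP never repeats the persistence rule.

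Persistent CIS might also be read as one kind of recurrence event, because 10.1 records it when describing stage at recurrence or progression and places the dating rule in the paragraph on confirmation dates. That reading is possible, but the separate definition points the other way and the SAP does not direct it.

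SAP 7.1 rule 1 also leaves out progression and death, which SAP 2.1 plainly treats as failures. So the missing persistence rule looks like loose shorthand rather than a decision to credit late clearance. That is fair, and the repair should cover all three.

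The short DFS definition is already in protocol 12.5.2.3, so the split lies within the protocol as well as between the documents. SAP 5.5 confines p-values to the primary analysis, so the SAP 7.2 part bears mainly on estimates. The route to a literal success is also narrow: under section 6.3, disease assessments stop for patients with recurrent or progressive disease who leave study treatment, so the case arises mainly among those who continue.

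A reader might go further and want a rule for cystectomy, or want to count against patients whose CIS cleared by 6 months after a TURBT or fulguration. The documents support neither as part of this point. Cystectomy is a separate gap with no effect shown here, and section 12.5.2.4 deliberately credits CIS cleared by 6 months.

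**Conclusion.** The conflict is real and lies in the text. Protocol 10.1, 12.5.2.4 and 3.1 together indicate failure from randomization. Protocol 12.5.1.1 and SAP 2.1 do not list persistent CIS, SAP 7.1 read literally credits a patient cleared after 6 months, and SAP 7.2 censors a patient for whom 12.5.2.4 requires an event at time zero.

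A reader might infer that the primary result will be wrong, or that it will favour the vaccine. The documents do not support either. An analyst who follows section 3.1 would score failure. The number of affected patients is not given, and the direction depends on which arm has more of them. CIS is a stratification factor, so its share should be roughly balanced, but late clearance need not be. What can be said is that each such patient is worth 4 points in an arm of 25, enough to change the test in a close result. This should be corrected before unblinding as a wording conflict; it is not a demonstrated bias.

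**What to change.** Before unblinding:

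1. In protocol 12.5.1.1 and SAP 2.1 and 7.1, list persistent CIS at 6 months, as defined in protocol 10.1, as a failure of 1-year DFS whatever the later status. In SAP 7.1 rule 1, add progression and death at the same time.
2. In protocol 12.5.2.3 and SAP 2.1 and 7.2, count persistent CIS as a DFS event at randomization, in line with protocol 12.5.2.4, and not as a censored observation.
3. Keep the credit for CIS cleared by 6 months.

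The cost is a few lines of wording. No new data are needed, because section 10.1 already has persistent CIS recorded as its own category. The downside is that reported 1-year DFS may be slightly lower, by 4 points in an arm of 25 for each patient it applies to.
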